### **4.7 Adverse Events and Reporting**

#### **4.7.1 Definition of Adverse Event (AE)**

Any untoward medical occurrence in a clinical study where participants are administered a medicinal product, which does not necessarily have to have a causal relationship with participation in this study.

An AE includes:

- Exacerbation of pre-existing illness
- Increase in frequency or intensity of a pre-existing episodic event or condition
- Condition detected or diagnosed after study intervention even though it may have been present before the start of the study
- Continuous persistent disease or symptoms present at baseline that worsens following the start of the study

An AE does not include:

- Medical or surgical procedure (e.g. surgery, tooth extraction) but the condition that leads to the procedure is an AE
- Pre-existing disease or conditions present or detected at the start of the study that did not worsen
- Situations where an untoward medical occurrence has occurred (e.g. hospitalisations for cosmetic elective surgery)
- Disease or disorder being studied, or sign or symptom associated with the disease or disorder unless more severe than expected for the participant's condition
- Overdose of concurrent medication without any signs or symptoms

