## 4.4 Risk Management

### 4.4.1 Cardiovascular Risk

Participation in aerobic exercise may increase the risk of cardiovascular complications such as cardiac ischaemia, arrhythmia or hypotension. The use of an appropriate graduated warm-up and cool-down is recommended to minimise these risks (ACSM, 2021). In the proposed study, participants' physiological response to exercise will be closely monitored during and after exercise. Exercise will be stopped if any adverse signs or symptoms occur (see table above). The researcher is experienced in the provision of clinical exercise tests and is trained in cardiopulmonary resuscitation.

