#### *4.7.5 Definition of Serious Adverse Event (SAE)*

Any untoward and unexpected medical occurrence or effect that:

- Results in death
- Is life-threatening – refers to an event in which the subject was at risk of death at the time of the event; it does not refer to an event which hypothetically might have caused death if it were more severe
- Requires hospitalisation, or prolongation of existing inpatients' hospitalisation
- Results in persistent or significant disability or incapacity
- Is a congenital anomaly or birth defect

An SAE form will be completed and forwarded to the sponsor or delegated representative within 24 hours. However, relapse and death and hospitalisations for elective treatment of a pre-existing condition do not need reporting as SAEs. All SAEs should be reported to the study sponsor local Research Ethics Committee where in the opinion of the Chief Investigator, the event was:

- 'Related', i.e. resulted from the administration of any of the research procedures; and
- 'Unexpected', i.e. an event that is not listed in the protocol as an expected occurrence

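### The AE definition contradicts itself and refers to a medicinal product the study does not give, and including unexpectedness in the SAE definition lets a serious but foreseen test-related event miss the 24-hour form

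*Protocol*

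**What the plan says.** Protocol section 4.7.1 opens its AE definition with "Any untoward medical occurrence in a clinical study where participants are administered a medicinal product". Its list of inclusions has two entries that matter here: "Condition detected or diagnosed after study intervention even though it may have been present before the start of the study" and "Continuous persistent disease or symptoms present at baseline that worsens following the start of the study". Its list of what is not an AE contains "Situations where an untoward medical occurrence has occurred (e.g. hospitalisations for cosmetic elective surgery", and also the disease under study or a "sign or symptom associated with the disease or disorder unless more severe than expected for the participant's condition".

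Section 4.7.5 defines an SAE as "Any untoward and unexpected medical occurrence or effect that" meets one of the usual seriousness criteria, and asks for an SAE form to reach the sponsor within 24 hours. Further down, the same section limits ethics committee reporting to SAEs judged both related and unexpected. There it explains unexpected as not being listed in the protocol as an expected occurrence.

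Sections 4.7.2 and 4.7.4 say that events are recorded regardless of whether they were expected.

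Sections 4.4.1 to 4.4.4 name the foreseeable harms. For the heart and circulation the text is "Participation in aerobic exercise may increase the risk of cardiovascular complications such as cardiac ischaemia, arrhythmia or hypotension". The others are muscle strain, post-exertional malaise and bruising after blood sampling.

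**The concern.** The definitions decide what sites write down as an AE and what they send to the sponsor quickly. Three faults make that depend on the reader.

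- The opening condition belongs to a drug trial. The procedures here are exercise tests, functional tests and blood sampling, in a study that the synopsis and section 3.0 call observational and section 4.7.6 treats as non-CTIMP.
- One exclusion bullet, taken as written, removes exactly what the opening line defines.
- Expectedness appears twice in section 4.7.5, once inside the SAE definition and once as a reporting filter. Used in the definition, it can stop a serious event from becoming an SAE at all.

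At stake are consistent AE classification across sites in three countries and prompt sponsor notice of a serious event after a maximal exercise test.

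**Working it through.** The protocol states no figure on this point, so the check sets the sections side by side.

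**1. Medicinal product.** Section 4.7.1 presupposes one. The synopsis describes exercise tests on two consecutive days with follow-up, and section 4.7.6 uses the SAE form for non-CTIMP studies. The opening condition does not fit the study.

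**2. The exclusion bullet.** The opening line makes an untoward medical occurrence an AE, and the bullet says a situation in which one has occurred is not an AE. Both cannot hold. The bullet's example, admission for elective cosmetic surgery, is a case in which nothing untoward happened. That points to a dropped negative.

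**3. Post-exertional malaise.** Take a participant with baseline fatigue that worsens after the test.
- Under the worsening-symptoms bullet, this is an AE.
- Under the disease-under-study bullet, it is not an AE unless more severe than expected for that participant.
- Section 4.4.3 says malaise occurs in this population, especially with incremental exercise, so a site could regard some worsening as expected.
- Section 4.7.1 does not say which bullet prevails or what level is expected.

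**4. A serious, foreseen event.** Take a hospitalisation for arrhythmia after the exercise test.
- Seriousness: met (hospitalisation, section 4.7.5).
- Unexpectedness: open to dispute, because section 4.4.1 names arrhythmia as a risk of exercise.
- If a site judges it expected, the event fails the SAE definition. The 24-hour form is not triggered. Nor is the 7-day rule in section 4.7.6, which applies to fatal or life-threatening SAEs.
- The event is still an AE (detected after the study intervention) and goes on the CRF under section 4.7.4. Sections 5.0 and 6.2 keep paper CRFs at the sites until the study ends, so the CRF alone gives no early central view.

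**5. Where expectedness is needed.** The related-and-unexpected filter in section 4.7.5 already applies it to ethics committee reporting. If every SAE were unexpected by definition, that half of the filter would do nothing. The word in the definition is therefore redundant at best.

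**6. Scale.** With 150 participants completing both tests, there are 150 x 2 = 300 tests. Section 4.3 cites 0 to 5.2 non-fatal adverse events per 10,000 tests, mostly in cardiac patients. Applied here as a rough guide, 300 x 5.2 / 10,000 = 0.156, so 0 to about 0.16 expected events. The cited upper figure for deaths is 1 per 10,000, and 300 x 1 / 10,000 = 0.03. The protocol gives no rate for post-exertional malaise, so none is calculated.

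**The case against.** A reader might infer that the named harms fall outside both definitions altogether, so that no event could count as an AE and no serious event of a named kind as an SAE. The document does not support that. The inclusion list in section 4.7.1 covers worsening symptoms, exacerbation of existing illness and conditions found after the study intervention. Section 4.7.4 requires all AEs on the CRF and asks participants about them at follow-up. Most sites would see that a negative had been lost. On the AE side, the text contradicts itself rather than excluding the harms.

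On the SAE side, no list in the text at hand is labelled as expected occurrences. The risk sections speak of possible increases in risk, and the explanation of unexpected is attached to the ethics committee filter, not to the definition. So the loss of the 24-hour form is one plausible reading, not a certainty. This does not rescue the wording: if the named risks are not the expected occurrences, nothing in the text shows what is, and the site still has to guess. Section 4.7.4 also sends AEs and SAEs through local procedures and on to the sponsor's research office without delay, which limits the harm but sets no fixed time.

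It is also fair to say that post-exertional malaise is captured whatever its AE label. Its prevalence is a secondary aim, and symptom profiles, diaries and wellness scores follow the tests. The protocol states no safety-rate aim or analysis, so a claim that a planned safety estimate would be biased has no basis here. Recording every episode of malaise as an AE is partly a choice. What needs correcting is that the two bullets can give different answers.

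**Conclusion.** The point holds as a wording fault with a practical consequence. Section 4.7.1 does not fit a study without a medicinal product, contains a bullet that negates its own definition, and leaves the AE status of post-exertional malaise to each site's reading. Section 4.7.5 allows a serious event of a foreseen kind to be classed as not an SAE and so to bypass the 24-hour form, although it would still be recorded as an AE.

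The SAE part matters most. It rests on the assumption that a site could treat the risks named in section 4.4 as expected. That is reasonable but not compelled by the text. In size it concerns how any single serious event is handled: over 300 tests, the protocol's cited rates suggest well under one such event, with the caveat that those rates come mostly from cardiac patients. The AE part affects the consistency of counts across sites by an amount that cannot be stated from the document.

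**What to change.** In section 4.7.1:
- Replace the medicinal-product phrase with *undergoing study procedures*.
- Restore *not* in the exclusion bullet, so that it covers situations in which no untoward occurrence has taken place.
- Reconcile the worsening-symptoms and disease-under-study bullets with one stated rule, so that all sites classify post-exertional malaise the same way. Which rule is the sponsor's choice.

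In section 4.7.5, delete *and unexpected* from the SAE definition and keep expectedness only in the related-and-unexpected filter for ethics committee reporting.

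The cost is a wording amendment to two sections and matching text on the AE form, with possibly a few more entries or SAE forms. No visits, procedures or staff are added.

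A separate inconsistency can be settled in the same edit: section 4.7.5 lists death as a seriousness criterion and then says that relapse and death need not be reported as SAEs. Those two statements must also be reconciled.

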#### *4.7.2 Non-serious AEs*

All such events, whether expected or not, should be recorded.

#### *4.7.3 Abnormal Baseline Findings*

Abnormal findings at that are deemed to be a clinically significant abnormality may be reported as an AE, according to the judgement of the Chief Investigator taking into account any associated clinical symptoms/signs from the below measures during pre; mid and post time frame.

#### *4.7.4 Reporting Procedures for All AEs*

Aim: to describe adverse events relating to study and the reporting process

Adverse event (AE) and Serious Adverse Event (SAE) will use the local NHS Trust reporting procedures but reported to the University of Derby Research and Knowledge Exchange Office as soon as possible.

All AEs should be reported on the CRF. Any questions concerning adverse event reporting should be directed to the Chief Investigator in the first instance. Participants will be asked to report AE's and SAE's during all follow up sessions. All participants will be provided with contact details for a trial phone, where they can communicate AE/SAE throughout the study and will be operated during working hours (Monday to Friday 9-5). Outside of these working hours, participants are encouraged to leave a voicemail and the study team will contact them back as soon as possible during working hours.

The following information will be recorded: description, date of onset and end date and severity. Follow-up information should be provided, as necessary. AEs considered related to the study as judged by a medically qualified investigator ([name], CI) or the sponsor will be followed until resolution or the event is considered stable. All related AEs that result in a participant's withdrawal from the study or are present at the end of the study, should be followed up until a satisfactory resolution occurs. It will be to the responsibility of the Chief Investigator's clinical judgement whether an AE is of sufficient severity to warrant removal from the study. The relationship of AEs to the study will be assessed by a medically qualified investigator. All such events, whether expected or not will be recorded.

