Description of interventions	Consecutive day 2 day CPET and follow up for 7 days for subjective feelings/fatigue.
Duration of study	
Study Duration:
 
 
- Total trial duration 12 months 
 
○ Recruitment 6 months (November 2022 to April 2023)
 
○ Data Collection (November 2022-April 2023)
 
○ Analysis and reporting: 4 months (April 2023-July 2023)
 
 
 
- Participant Duration: 3 sessions (1 Familiarisation, 2 CPET on consecutive days) and 1 week follow up
 

Randomisation and blinding	None

Study Investigators	
Chief Investigator: [name] Senior Lecturer in Exercise Physiology School of Human Sciences University of Derby, UK	Principle Investigator (Sheffield, UK) [name] Senior Research Fellow Advanced Wellbeing Research Centre Sheffield Hallam University, UK
Principle Investigator (Chicago, USA) [name] Clinical Associate [name] of Physical Therapy University of Illinois at Chicago Chicago, USA	Principle Investigator (Bengaluru, India) [name] [name] Assistant Professor, Department of Physiotherapy Ramaiah Medical College, Bengaluru, India
Co-Investigator: [name] [name] of Physical Therapy University of Illinois at Chicago Chicago, USA	Co-Investigator: [name] Lecturer in Exercise Physiology School of Human Sciences University of Derby, UK
Co-Investigator: [name] Director, Advanced Wellbeing Research Centre Sheffield Hallam University	Co-Investigator: [name] Consultant Respiratory Physician University Hospitals of Derby and Burton Derby, UK
Co-Investigator: [name] Assistant [name] of Physical Therapy University of Illinois at Chicago Chicago, USA	Co-Investigator: [name] School of Human Sciences University of Derby
Co-Investigator: [name] Researcher, Advanced Wellbeing Research Centre, Sheffield Hallam University.	Co-Investigator: [name], Principal Research Fellow, Advanced Wellbeing Research Centre, Sheffield Hallam University.
Co-Investigator: [name], Associate Professor, Advanced Wellbeing Research Centre, Sheffield Hallam University.	Co-Investigator:

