## **4.0 Study Protocol**

Each test will be interpreted following published guidelines provided by the American College of Sports Medicine. Upon the conclusion of each test, the key descriptive characteristics and findings will be recorded to facilitate the use of cohort analyses. Data will be stratified according to the demographic (age, gender, ethnicity, pre-COVID-19 functional status and important physiological parameters for a given workload (absolute and relative oxygen consumption or  $VO_2$  peak,  $O_2$  pulse, alveolar-arterial  $O_2$  gradient, arterial to end-tidal  $CO_2$  difference and the relationship between carbon dioxide output and ventilation ( $V_E/VCO_2$  slope))). These approaches will be used to identify differences, trends and patterns in key defining variables that might lead to longstanding impairment/morbidity. Study day 1 will be conducted 7-10 days post baseline measures to ensure no symptoms of post exertional malaise and/or excessive fatigue from baseline assessments. Patients will wear accelerometers during this period to compare baseline and follow up.

Baseline	Session 2	Session 3 (+1 day)	7 Day follow up
Anthropometrics Questionnaires Symptom Profile* Lung Function TUG 6MWT	Symptom Profile* ECG Resting HR + BP CPET Lactate and BP Recovery following CPET HRV	Symptom Profile* ECG Resting HR + BP CPET Lactate and BP Recovery following CPET HRV	Accelerometry Patient Log/Diary HRV

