### **4.1.3 Functional Status**

Two different assessments of lower extremity functional capacity will be conducted at each visit these are (A) the 6-minute walk test (6MWT) and (B) the timed up and go test (TUG). The 6MWT is a standardised and widely used measure of functional status in individuals with chronic disease such as chronic obstructive pulmonary disease, cystic fibrosis, congestive cardiac failure, peripheral vascular disease, and elderly. It has been previously used to assess response to interventions and predict morbidity and mortality. Participants will be given a shortened practice attempt (1-2 minutes) at the beginning of each of their assessment visits. This will not be recorded but will be performed to allow familiarisation with the assessment and repeated at each visit for

consistency. Patients suffering from excessive fatigue/Post exertional malaise from the 6MWT will be excluded from the study to prevent further onset of these symptoms.

The TUG is reliable and reproducible and has been validated as a predictor of frailty and risk of falls in elderly adults. The TUG has several advantages over other measures, mainly its reproducibility and shorter assessment time. Its use at predicting functional status following pneumonia has not been assessed previously.

Participants will also be asked to self-report their return to functional activity and employment at each contact with the research team (telephone consultations and follow-up visits.) Each participant will be asked at each contact with the research team if they have returned to perform their activities of daily living to the same level as 6 weeks before admission, and if they have returned to their occupation (if employed.) The patient-reported date of return to these activities will also be recorded.

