## 4.2 Follow-up Assessments

Using a custom developed application alongside commercially available heart rate monitoring devices, participants will be asked to provide accelerometry (asked through the participants phone), heart rate variability (iHeart) and a subjective wellness score for each day following baseline and CPET investigations each for a period of 3 days. This custom developed software has been developed at the Advanced Wellbeing Research Centre to provide objective and subjective assessment of fatigue in people suffering with long covid and has successfully been piloted with over 200 individuals. Where smartphone data is not possible, individuals will be asked to wear an accelerometer and subjectively report their wellness through patient diary.

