## 9.0 End of Study

The end of the study is the date of the home visit (post-study follow up) of the last participant enrolled.

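### The follow-up contacts and durations in the protocol do not agree, leaving adverse-event enquiry after the second CPET with no defined contact and the end of study with no scheduled event

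*Protocol*

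**What the plan says.** The synopsis gives participant duration as "3 sessions (1 Familiarisation, 2 CPET on consecutive days) and 1 week follow up" and describes the procedures as "Consecutive day 2 day CPET and follow up for 7 days for subjective feelings/fatigue". The schedule table in section 4.0 has four columns: baseline, Session 2, Session 3 one day later, and a 7-day follow-up. The last column contains only "Accelerometry Patient Log/Diary HRV".

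Section 4.2 describes how these data are collected: by phone app and heart-rate device, or by accelerometer and diary where a smartphone cannot be used. It asks for "a subjective wellness score for each day following baseline and CPET investigations each for a period of 3 days".

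Three other provisions depend on follow-up contacts:

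- Section 4.7.4, on harms: "Participants will be asked to report AE's and SAE's during all follow up sessions". It adds a route that the participant must start: "All participants will be provided with contact details for a trial phone, where they can communicate AE/SAE throughout the study". That phone is staffed in office hours on weekdays and takes voicemail otherwise.
- Section 4.1.3, on return to daily activities and work, which is asked "at each contact with the research team (telephone consultations and follow-up visits".
- Section 9.0: "The end of the study is the date of the home visit (post-study follow up) of the last participant enrolled".

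**The concern.** Harms questioning, return-to-function reporting and the end-of-study date each point to a kind of contact that the schedule does not show after Session 3. A site that follows the table would see the participant for the last time at the second maximal test and would then receive only device and diary data.

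Two things are at stake. The first is ascertainment of harm. Section 4.4.3 recognises that post-exertional malaise occurs in long COVID, particularly with incremental exercise, so the days after the second test matter most. If the team schedules no enquiry there, later events are recorded only when a participant volunteers them, and those who feel worst may be least likely to call. The second is the study end date. Under sections 5.0 and 6.2 the paper CRFs stay at site until that date and are then sent for data entry. Under section 4.7.4, related events still present at the end of the study must be followed to resolution. Both need a date that the schedule can produce.

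**Working it through.** The protocol gives no figure to reproduce. The check sets the named contacts against the schedule and adds up the timeline.

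**Timeline, with baseline as day 0**

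- Section 4.0 puts the first CPET 7 to 10 days after baseline, so Session 2 is on day 7–10.
- Session 3 is one day later: 7 + 1 = 8 to 10 + 1 = 11, so day 8–11.
- With 7 days of follow-up (synopsis, section 4.0 table): 8 + 7 = 15 to 11 + 7 = 18, so it ends on day 15–18.
- With 3 days of follow-up (section 4.2): 8 + 3 = 11 to 11 + 3 = 14, so it ends on day 11–14.

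The two durations put the last scheduled data point four days apart for the same participant.

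**Contacts named in the text against contacts in the schedule after Session 3**

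| Provision | Contact it relies on | In the schedule after Session 3? |
|---|---|---|
| 4.7.4, AE/SAE questioning | follow-up sessions (number, timing and mode not given) | no session; remote recording only |
| 4.1.3, return to function | telephone consultations, follow-up visits | neither |
| 9.0, end of study | home visit | no |

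Staffed visits or calls scheduled after Session 3: 0.

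**Does another section fill the gap?**

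- Section 4.4.3: the team follows participants up after baseline and before the CPETs, so this does not reach the period after the second test.
- Section 4.1.6: blood sampling continues for 30 minutes after exhaustion, so it ends on the day of the test.
- Section 10.0: a follow-up call is arranged for anyone withdrawn because of an adverse event, so the event must already be known.
- Section 4.7.4: the trial phone is available throughout, but the participant has to start the contact.

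**Two readings of follow-up sessions in section 4.7.4**

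- If the term means Sessions 2 and 3, the last enquiry falls on the day of the second CPET and cannot capture later effects.
- If it means the 7-day diary period, no AE question is listed for it and nobody is assigned to review entries and carry them to the CRF. Section 4.7.4 requires a description, onset and end dates, and severity for each event; a daily wellness score does not supply these.

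On either reading, no contact that actively asks about adverse events after the second CPET is defined.

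**The case against.** A reader might infer that nobody asks participants about harm after the second test. The text does not support that. Section 4.7.4 says they will be asked, and there is a follow-up period with a diary and a daily wellness score, which may be what that section has in mind. The defect is that the contact and its mode are not fixed.

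A reader might also infer that the home visit never takes place. Section 9.0 names it; its absence from the table shows that two sections disagree, not which of them is wrong. Likewise, return to function is not tied only to missing contacts: it is to be asked at every contact, which can include Sessions 2 and 3, although those reach only day 8–11.

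The harm argument has a limit as well. Section 4.7.1 counts worsening of baseline symptoms as an adverse event, but leaves out symptoms of the disease under study unless they are worse than expected. Some post-exertional worsening may therefore not be an AE at all, and the diary and wellness score do capture it as data. This weakens any claim about how many events would be lost. It does not remove the gap, because judging whether symptoms are worse than expected requires someone to ask about their severity.

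The safeguards are real: the phone line with call-back, follow-up of related events, and monitoring after each test. Apart from that same-day monitoring, they act only once an event has been reported.

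**Conclusion.** The point holds as an inconsistency within the protocol that has practical consequences. The synopsis and sections 4.0, 4.1.3, 4.2, 4.7.4 and 9.0 describe different follow-up contacts and two different durations. Followed as scheduled, the plan leaves adverse events arising after the second maximal test to spontaneous reporting in all 150 planned participants, and ties the study end date to a visit that the schedule does not contain.

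The number of events that would be missed cannot be derived from the document, and none is claimed. The conclusion assumes that the section 4.0 table and section 4.2 list every planned contact, and that the study end date in sections 5.0 and 6.2 is the one defined in section 9.0. If site instructions already provide a call or home visit, the remedy is only to write it into the protocol. The contact schedule, AE ascertainment and end-of-study definition belong in the protocol, so a statistical analysis plan would not settle this. It should be corrected.

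**What to change.** 1. State one follow-up duration and use it in the synopsis, the section 4.0 table and section 4.2.
2. Add an explicit AE/SAE and return-to-function enquiry to the 7-day follow-up column. At minimum, make it a compulsory item in the existing app or diary that covers the whole follow-up period, with named site staff reviewing entries and transcribing events to the CRF. A telephone call by the site team is the alternative.
3. Point sections 4.1.3 and 4.7.4 to that enquiry by name.
4. In section 9.0, either put the home visit in the schedule or define the end of study as the last participant's completion of the scheduled follow-up.

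Cost: protocol wording plus a small diary and review burden. If done by telephone, at an assumed 10 minutes per call (the protocol gives no figure), 150 × 10 = 1,500 minutes, or 25 staff hours in total. A few more adverse events may be recorded. No exercise procedure or stopping rule changes.
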